Hypothesis Aim 1: Community engagement and mixed methods data will yield insights into current treatment seeking patterns and needs for AGYW and effective adaptation strategies to improve the proposed intervention.

Aim 2: Implement a pilot of the intervention and assess implementation outcomes.

The provider and staff component will consist of two groups to facilitate participation and accommodate provider/staff schedules. Four separate groups of AGYW will participate in the adolescent health club component, using a wait-list control group design. Separate groups are needed due to the group nature of the intervention activities which limits the number of people who can participate at one time. Intervention participants will be surveyed pre- and post-intervention to examine acceptability, feasibility, and uptake. Qualitative process data will also be collected and analyzed.

Hypothesis Aim 2: AGYW's satisfaction with services will improve 20% post-intervention compared to pre-intervention.

Aim 3: Assess a pilot set of health outcomes for future research.

Quantitative pre- and post-tests will also assess pilot effectiveness health and behavioral outcomes.

Hypothesis Aim 3: Sexual and reproductive health (SRH) knowledge will show statistically significant improvement post-intervention. Behavioral elements of SRH will show positive trends, but will not be statistically significant.

2. **Probable Duration of Project:** State the expected duration of the project, including all follow-up and data analysis activities.

5-6 years

3. **Background:** Describe the background information that led to the plan for this project. Provide references to support the expectation of obtaining useful scientific data.**A.1. Status of adolescent sexual and reproductive health (SRH) and adolescent-friendly health services**

Most of the over one billion people between the ages of 15-25 in the world live in low- and middle-income countries (LMICs). Among youth living in LMICs, 70% are in Asia.⁽¹⁾ Among health, education, and employment challenges facing young people, SRH need specific action.⁽²⁻⁷⁾ Adolescent girls and young women (AGYW) are particularly vulnerable with adolescent pregnancy, maternal morbidity and mortality, STIs/HIV, gender-based violence, and psychological trauma stemming from these issues given their precarious status in patriarchal cultures.⁽⁸⁻¹¹⁾ While striving to achieve the Millennium Development Goals, the global health agenda largely

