Survey with AGYW on care-seeking patterns and perceptions of healthcare quality and quantitative analysis: A random sample of AGYW seeking care at a set of public (N=3) and private (N=3) healthcare facilities in the study area will be selected and asked to participate in a brief, 20-30 minute survey using validated measures^(32, 45, 110) to discuss their patterns of healthcare-seeking (where they go for different problems, and what influences those choices), and their perceptions and experiences with adolescent healthcare. For unmarried participants under the age of 18, consent will be obtained from both a parent and the young woman. My collaborators and I have experience working in the study area and obtaining consent from parents, and we do not anticipate challenges obtaining consent. I will survey 20-25 AGYW from each facility, with a total N=100-150. Survey data will be entered into R,⁽¹¹¹⁾ and bivariate and multivariate analyses will be conducted to understand factors associated with AGYW treatment-seeking that may need to be addressed in the health clubs. Analyses will also explore quality of care to identify elements that may need to be incorporated into the provider sensitization. This survey will allow me to apply skills gained in Training Aim 1.

ADAPT-ITT Adaptation, Administration, and Production Phases

Theater testing with key stakeholders for intervention adaptations: Theater testing meetings will be held in which intervention sessions are presented and, in some cases, acted out to the group. Special attention will be given to adaptations needed due to COVID. Audience members' responses and post-meeting critiques of the material will be recorded and analyzed (see below). During the meetings, we will ask for both general feedback, as well as whether adolescent health club sessions need to be conducted separately with different age groups or based on marital status (married adolescents, regardless of age could have different needs than unmarried

adolescents). Separate meetings (up to 10 meetings total) will be held with the following stakeholder groups to present the intervention modules and elicit feedback on revisions or adaptations: 1) AGYW; 2) community members/KIIs; and 3) healthcare providers, CHVs, and NGO staff. Due to COVID, we will ensure groups remain smaller (no more than 5-10 participants) to allow adequate distancing. Additional meetings may be conducted after modifications are made to ensure agreement.

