
Table 1: Domains to be covered in AGYW pre- and post-intervention surveys.

Pre-Intervention Survey Domains	Post-Intervention Survey Domains

Demographics	Demographics
Clinic service uptake/use	Clinic service uptake/use ^(32, 130)
SRHR knowledge	SRHR knowledge ^(123, 131)
Violence and safety	Violence and safety ^(124, 125)
Gender norms	Gender norms ^(48, 132)
Agency	Agency ^(66, 133)
Mental health	Mental health ⁽¹²⁶⁾
	Intervention acceptability ⁽¹²⁹⁾
	Satisfaction with intervention/services ⁽¹²⁸⁾
	Feasibility ⁽¹²⁸⁾

Intervention Power Calculation and Sample Size Considerations: Power calculations and sample size for the adolescent health club component are determined based on the SRH knowledge measure.⁽¹²³⁾ With 85% power, in a two-arm comparison design (similar to round one in Figure 2 above), and based on data from a previous intervention study⁽¹³¹⁾ in which the investigators found a pre/post intervention difference of 1.3 and a standard deviation of 3, we will need 50 pairs or 100 participants in the adolescent clubs total. Broken into four groups, I plan for each group to be 25 participants. As this calculation does not take into consideration within-group analysis, it is a ≈20% overestimate, which allows for 20% loss to follow-up, or participant drop-out without loss of statistical power. However, to minimize bias, I am targeting 95% follow-up. 95% follow-up is based on our team's procedures for tracking and retaining adolescent health club participants. Specifically, we will make clear the participation expectations upon recruitment, consent, and the initial health club meeting. We will follow-up with participants who miss club sessions via cell phone and home visits as needed. These methods have been used by the research team in previous studies in the study area.

Implementation and Intervention Data Analysis

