Qualitative analysis: The observations and interviews conducted during and after the intervention will be transcribed, translated into English (as needed), and entered into the qualitative software analysis program Atlas.ti (v.8.1).⁽¹¹²⁾ A modified framework approach^(113, 115, 134) to coding will be used in which deductive themes will be developed *a priori* based on the study's conceptual framework and implementation indicators, and inductive codes will be developed and applied iteratively based on review of the transcribed documents. Text will then be reviewed for patterns of consistency, variation, relationships between themes and exemplary cases or quotations. Qualitative data will also be merged with the quantitative findings to triangulate results and further contextualize the quantitative indicators, in keeping with a parallel mixed methods design.^(114, 116, 135)

Quantitative analysis: I will use R to analyze the data. Descriptive statistics will be obtained for continuous and categorical variables. The health outcome scales to be used in this study are well-validated (in contrast to the implementation outcome scales), and can be assumed to have approximate normal distributions, although these assumptions will be checked. This study will conduct both within and between-group analyses for the adolescent club component. All subjects will have pre- and post-treatment within-subject measures, and these comparisons can be preliminarily analyzed with paired t-tests. Primary analyses will focus on using repeated measures general linear mixed models to examine comparisons across recruitment cohorts. We will also be able to compare the treated participants from group 1 with the untreated participants in group 2, followed by the group 2 treated participants with the untreated group 3 participants, and finally the group 3 treated participants with the untreated group 4 participants, and can use repeated general linear mixed models for this unbalanced design.

5. Genetic Testing N/A

A. Describe

- i. the types of future research to be conducted using the materials, specifying if immortalization of cell lines, whole exome or genome sequencing, genome wide association studies, or animal studies are planned *Write here*
- ii. the plan for the collection of material or the conditions under which material will be received *Write here*
- iii. the types of information about the donor/individual contributors that will be entered into a database *Write here*

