For the provider/staff sensitization component, a total of N=60 providers and staff will be recruited from the public and private clinics where AGYW were recruited for the formative quantitative survey. There will be two separate groups of 20 people each who undergo the sensitization workshop. The workshop will take place over four days. In previous work in the study area, retaining providers for a short intervention such as the one described in this proposal has not been a challenge and therefore we anticipate no challenges in recruiting the required sample size.

For the adolescent health club component, households with AGYW between the ages of 15 and 25 will be identified by Apnalaya's field team from randomly selected block sectors of the study area. AGYW and their mothers (if unmarried and under the age of 18) will be approached by a member of the research team and the adolescent health club intervention will be explained. If consent is obtained, the AGYW will be enrolled to either participate in the health club immediately or join the wait-list. An initial sample of 50 AGYW will be recruited (one group of 25 to begin intervention immediately, and one wait-list group). After the first intervention group has completed the health club curriculum, the wait-listed group will begin the intervention, and another 25 AGYW will be recruited for a wait-list. This will continue until four groups of 20-25 AGYW complete the health club intervention. Factoring in an attrition rate of 20%, the expected N at endpoint is 80. AGYW will complete the pre-intervention evaluation instrument upon enrollment. When young women complete the health club curriculum, they will also complete the post-intervention evaluation instrument. A sub-sample of young women will be asked

to participate in a focus group discussion to reflect on the club's impact and acceptability. To limit differences in

the time needed to assemble the health club groups, we will avoid recruiting during busy religious festivals/holidays (such as Ramadan) or vacation periods.

b. Describe how potential subjects are contacted.

Key informants and healthcare providers/staff for all phases will be contacted in the following ways: through in-person meetings, and snowball referrals/introductions via email (email recruitment template is attached) or cell phone.

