 No
- Will the waiver adversely affect subjects' rights and welfare? YES NO
- Why would the research be impracticable to conduct without the waiver? *Write here*
- Where appropriate, how will pertinent information be returned to, or shared with subjects at a later date?
Write here

SECTION IV: PROTECTION OF RESEARCH SUBJECTS**Confidentiality & Security of Data:**

1. What protected health information (medical information along with the HIPAA identifiers) about subjects will be collected and used for the research?

During the formative data collection, no names will be collected. Email addresses and/or cell phone numbers may be collected and used to facilitate recruitment and interview/survey data collection. After the interview or survey is completed, any cell phone or email information collected will be destroyed. Contact information will not be linked to phase 1 interview or survey responses.

During the intervention phase (both the facility-based and adolescent/community-based intervention), cell phone numbers may be collected and used to: facilitate recruitment, notify participants about intervention session scheduling, and/or follow-up with intervention participants who miss a session. After a participant's participation in the intervention is completed, any email or cell phone information collected will be destroyed. The PI will review intervention survey data within 48 hours from the time it is collected to determine if there are any immediate mental health concerns (i.e., a high score on a mental health measure indicating severe psychological distress), and if needed link the participant with additional services.

Due to the group nature of the intervention components, participants will meet each other in person, and may disclose identifiable information to other participants. Since the project will not be able to ensure the confidentiality of participant's responses, members of the group will be reminded of the confidential nature of the discussion and will be cautioned not to discuss any conversations or individual responses outside of the group. A unique numerical code will be assigned to intervention participants and used to link their pre- and post- intervention information. Contact information will not be linked with pre- and post-intervention surveys.

2. How will the research data be collected, recorded and stored?

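### Aim 2 predicts a 20% pre-to-post rise in satisfaction with services, but satisfaction is listed only in the post-intervention survey and no baseline measure is named

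*Combined protocol and SAP*

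**What the plan says.** Section I, item 1 (Statement of Purpose) gives Aim 2 a single hypothesis: young women's "satisfaction with services will improve 20% post-intervention compared to pre-intervention". The Aim 2 description just before it says intervention participants will be "surveyed pre- and post-intervention to examine acceptability, feasibility, and uptake"; satisfaction is not in that list.

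Table 1 in Section I, item 4 (Research Plan) sets out the survey domains in a pre column and a post column. "Satisfaction with intervention/services" appears in the post column only. "Clinic service uptake/use" appears in both. The pre-intervention survey is completed at enrollment and the post-intervention survey when the curriculum ends.

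The quantitative analysis paragraph in the same item states: "All subjects will have pre- and post-treatment within-subject measures". It proposes paired t-tests as a preliminary step and mixed models as the main analysis. Neither that paragraph nor Section I, item 13 (Statistical Considerations) says how the 20% will be calculated.

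**The concern.** A claim of improvement from before to after needs a measurement before. The hypothesis and the table of survey domains do not fit together: one assumes a baseline satisfaction value, and the other provides for none.

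The target is numerical and is the only hypothesis given for Aim 2. It also bears on the provider workshops. Section I, items 4 and 13 say that component will be judged mainly through the young women's outcomes, and background section A.4 cites improved client satisfaction as the evaluation result for packages that included that curriculum. If the baseline is not collected, it cannot be recovered by asking women after they have been through the club. Section IV, item 1 also has contact details destroyed once participation ends.

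**Working it through.** The plan has no calculation for satisfaction to reproduce. Its sample size rests on the sexual and reproductive health knowledge measure. The check is therefore mainly a comparison of the plan's own statements.

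**1. Table 1, row by row**

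| Domain | Pre | Post |
|---|---|---|
| Demographics | yes | yes |
| Clinic service uptake/use | yes | yes |
| Knowledge | yes | yes |
| Violence and safety | yes | yes |
| Gender norms | yes | yes |
| Agency | yes | yes |
| Mental health | yes | yes |
| Acceptability | no | yes |
| Satisfaction | no | yes |
| Feasibility | no | yes |

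Post-only domains: 10 − 7 = 3. This is unlikely to be a layout accident. The three rows sit together, and the other two concern the intervention itself, so placing them after exposure makes sense. The satisfaction row combines the intervention with services, whereas the hypothesis is about services alone.

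**2. Can the wait-list comparison supply the comparator?** The analysis paragraph compares treated women in one group with untreated women in the next. The text describes only two surveys per woman, at enrollment and at completion of the curriculum. Women still waiting have therefore answered only the enrollment survey, which lists no satisfaction domain. The between-group contrast has the same gap as the within-person one.

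**3. Can the formative survey supply it?** It takes "A random sample of AGYW seeking care at a set of public (N=3) and private (N=3) healthcare facilities" and asks about perceptions of care. Club members are instead recruited from households in randomly selected sectors. The samples differ, so this is not a within-person baseline. Linkage is also ruled out: "Contact information will not be linked to phase 1 interview or survey responses".

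**4. Does the satisfaction row name an instrument?** Its citation (reference 128) is listed as a systematic review of implementation-outcome instruments, so no specific questionnaire is identified.

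**5. Number of women affected.** Section III, item 3: "Factoring in an attrition rate of 20%, the expected N at endpoint is 80", that is 100 × 0.80 = 80. At the 95% follow-up target in Section I, item 4: 100 × 0.95 = 95.

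**6. What 20% could mean.** The plan gives no scale and no baseline level. Assume, for illustration only, a score from 0 to 100:

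- Baseline 50: relative target 50 × 1.2 = 60; absolute target 50 + 20 = 70.
- Baseline 70: relative target 70 × 1.2 = 84; absolute target 70 + 20 = 90.
- Highest baseline from which the target can be reached: relative 100 / 1.2 = 83.3; absolute 100 − 20 = 80.

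The two readings differ by 10 points at a baseline of 50 and by 6 points at 70.

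**The case against.** The best counter-argument is that a baseline may exist under another name. Table 1 lists domains; it is not the questionnaire. The repeated domain on clinic use cites references 32 and 130, both titled as measures of youth-friendly primary care services. The formative survey of perceptions and experiences of care also cites reference 32. The post-only row could then be read as satisfaction with the program, with experience of services carried in the repeated domain.

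This is a fair reading, and it means a missing baseline is not proved. But the plan labels that domain as use, lists satisfaction separately with a different citation, and never says which repeated items would form a satisfaction score. What stands is that the fix may need no new questions, only a sentence naming existing ones.

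Two supporting statements are weaker than they look. The Aim 2 list of what is surveyed pre and post is loose: it includes acceptability and feasibility, which Table 1 makes post-only, so the absence of satisfaction from it proves little. The analysis sentence on within-subject measures follows one about health outcome scales and need not mean that every domain is measured twice. The conclusion does not depend on either.

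It can also be said that this is a pilot, that sample size does not rest on satisfaction, and that evaluation instruments were to be revised after the formative work. All true, and they limit the reach of the problem. They do not give the stated hypothesis a baseline.

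**Conclusion.** The concern holds. Aim 2's one hypothesis calls for a pre-to-post change in satisfaction with services, and the plan designates no pre-intervention satisfaction measure for club participants. As written, the trial cannot say whether the 20% target was met. The undefined 20% is a second gap in the same hypothesis, and it would remain even with a baseline in hand.

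The reach is limited to this hypothesis, for all 80 to 95 women expected to complete. Acceptability, feasibility, uptake and the process data are unaffected. The conclusion rests on Table 1 and the surrounding text; the questionnaire items themselves are not shown. The 0-100 figures are illustrations on an assumed scale. This must be corrected, because the hypothesis otherwise has no designated data to test it.

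**What to change.** 1. Add the services-satisfaction items to the enrollment survey, with the same wording and recall window as in the post survey. Alternatively, name the items already repeated under clinic use that will form the satisfaction score.
2. Report satisfaction with services separately from satisfaction with the club. The latter stays post-only.
3. State whether 20% is relative or absolute, and on what score or proportion.
4. State how women with no clinic visit in the recall window are handled. The plan does not propose limiting the main analysis to women who used services at both times. If that is considered, it needs justification, because raising uptake is itself a goal of the intervention.
5. If baseline surveys are already complete and contain no such items, reword the hypothesis as a post-intervention target with no claim of change.

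The cost is a few extra items at enrollment, or none if existing items are named, plus wording changes to Table 1 and the hypothesis. Timing matters because enrollment is staggered: Section III, item 3 recruits 50 women first and the rest later, so items added after that first intake would give a baseline for at most 100 − 50 = 50 women. If baseline is complete, only the wording changes.

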materials such as tarps and pieces of wood or tin. Most men are engaged in daily low-wage work, with considerable unemployment. Only 28% of women work for cash income, typically sorting and recycling in a local dumping ground or selling embroidery work. The average monthly family income is INR 5900 (approximately US \$100/month). The population is young; 60.6% are under the age of 25. Among married women, 38% were married before the legal age of 18 years old, and only 5.5% of young women have studied beyond the 10th standard.⁽¹⁰³⁾ The Urban Health Center (UHC) in the study community is a government-funded primary care facility implemented with the Department of Preventive and Social Medicine at T.N. Medical College. The UHC, along with three smaller clinics (known as health posts), constitute the primary government healthcare for the study area. CHWs work out of the health posts and make door-to-door rounds to provide education and distribute basic interventions and medications. My mentors and I have partnered with the UHC in previous projects.^(66, 104, 105) The UHC is developing an adolescent-friendly health clinic, and being expanded. Healthcare is also provided through privately-funded NGO clinics, and a wide variety of private practitioners, primarily non-allopathic (e.g., *ayurvedic*, *unani*, and homeopathic), with about 10% allopathic providers. The private sector has collaborated with ICRW and myself in the past, vital prior relationships that will facilitate the present K01 study. Fieldwork conducted in 2014 found relatively fewer AGYW using private providers as most private sector providers are male. However, my recent discussions and observations suggest that more private providers are expanding their practices to include female nurses and medical assistants, suggesting that more AGYW may begin seeking care in this sector. Seven NGOs work in the community, and one will collaborate with this project. *Apnalaya*, working in the area since 1975, has extensive experience in providing health and social services as well as citizenship and life skills training to youth in the study community. I have previously collaborated with *Apnalaya*. In this project, *Apnalaya* will be involved in two ways. First, as a key NGO working with youth in the study area, one to two members of their team will be interviewed in the key informant interviews in the assessment/formative research phase, and invited to join the community advisory board (function of board described below). Second, they will provide support in recruitment of adolescent girls in the assessment/formative research phase. They routinely hold events with AGYW and provide some health and social services to community members. They will verbally announce/advertise the study to AGYW, and refer interested AGYW to our team for further information and enrollment. Their participation will be covered by the Tata Institute and Indian Council for Medical Research IRBs.

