For the adolescent health club component, the pilot study employs a waitlisted control group design. In this modified version of the stepped wedge design, all groups receive the intervention, and participants serve as their own controls. This design utilizes a smaller sample size of AGYW and fewer facilitators, making it more feasible for a K award, while still enabling all participants to participate in the intervention. The waitlisted control design also avoids some of the challenges associated with carryover effect that can occur in other crossover designs, as participants move unidirectionally from control to intervention. The adolescent health club curriculum (which takes approximately 2.5 months to complete) will be sequentially administered to four groups, each with a waitlisted control group. Individuals can be compared to themselves, and the other groups. Sequentially administering the intervention will be more feasible than administering the intervention simultaneously to separate neighborhood clusters, limiting the number of facilitators needed. Power calculations and sample size for the adolescent health club component are determined based on the SRHR knowledge measure. With 85% power, in a two-arm comparison design, and based on data from a previous intervention study in which the investigators found a pre/post intervention difference of 1.3 and a standard deviation of 3, we will need 50 pairs or 100 participants in the adolescent clubs total. Broken into four groups, this means that we will plan for each group to be 25 participants. As this calculation does not take into consideration within-group analysis, it is a slight overestimate, which allows for some attrition.

SECTION II: RESEARCH INVOLVING DRUGS, BIOLOGICS, RADIOTRACERS, PLACEBOS AND

If this section (or one of its parts, A or B) is not applicable, check off N/A and delete the rest of the section.

A. RADIOTRACERS

N/A

1. Name of the radiotracer: *Write here*

2. Is the radiotracer FDA approved? YES NO

If NO, an FDA issued IND is required for the investigational use unless RDRC assumes oversight.

3. Check one: IND# *Write here* or RDRC oversight (RDRC approval will be required prior to use)

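### The Aim 2 and Aim 3 hypotheses are worded as pre-to-post gains, and nothing in the plan says that the wait-list comparison decides them

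*Combined protocol and SAP*

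**What the plan says.** **Hypotheses (Section I, item 1).** For Aim 2, participants' "satisfaction with services will improve 20% post-intervention compared to pre-intervention". Aim 3 is introduced by "Quantitative pre- and post-tests will also assess pilot effectiveness health and behavioral outcomes", and its hypothesis is "Sexual and reproductive health (SRH) knowledge will show statistically significant improvement post-intervention". The Aim 2 paragraph mentions the wait-list design, but neither hypothesis refers to it.

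**Design (Section I, item 4, Study Design, repeated in item 13).** The club curriculum, about 2.5 months long, "will be sequentially administered to four groups, each with a waitlisted control group".

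**Analysis (Section I, item 4, Quantitative analysis).** Paired t-tests are preliminary. "Primary analyses will focus on using repeated measures general linear mixed models to examine comparisons across recruitment cohorts". The text then adds that treated group 1 can be compared with untreated group 2, treated 2 with untreated 3, and treated 3 with untreated 4.

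**Sizing (Section I, items 4 and 13).** A two-arm comparison at 85% power, with a pre/post difference of 1.3 and an SD of 3, gives 50 pairs or 100 participants in four groups of 25. Section III, item 3 expects 80 at endpoint.

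**Measurement.** The Adolescent Health Club paragraph of item 4 and Section III, item 3 describe two surveys: one at enrolment and one after the participant's own curriculum. Table 1 lists satisfaction only in the post-intervention column.

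**Setting (Section I, item 4, The Study Area).** "The UHC is developing an adolescent-friendly health clinic, and being expanded"; private providers are also reported to be adding female staff.

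**The concern.** The plan builds a wait-list control and then states its hypotheses without it. Aim 2 is explicitly post versus pre. Aim 3 asks for "statistically significant improvement post-intervention" and names neither comparator nor test. The analysis section does not say which of its three analyses (paired test, cross-cohort mixed model, treated-versus-untreated contrasts) settles either aim.

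A within-person change also picks up anything else that moves the score: repeating the same knowledge instrument, clubs attended elsewhere (which the plan intends to ask about), or change in local services. Groups 2 to 4, 75 of the 100 women, are surveyed at enrolment, wait while the previous club runs, and then attend their own. Their pre/post change therefore spans about 2.5 + 2.5 = 5 months, half of it untreated.

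At stake is the pilot's main finding. Aim 3 exists to inform future research, and an uncontrolled gain reported as the club's effect would be carried into that planning.

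**Working it through.** **Inputs.** From the sizing paragraph: difference 1.3, SD 3, power 85%, 100 enrolled, 25 per group. From Section III, item 3: 80 at endpoint. Alpha and sidedness are not stated, so two-sided 5% is assumed. The plan does not say whether 3 is the SD of scores or of changes; it is taken as the SD of change except where noted.

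**1. The plan's own figure.**
- Paired formula: n = [SD × (z0.975 + z0.85) / difference]² = [3 × (1.960 + 1.036) / 1.3]² = 47.8, so 48. The exact paired t calculation gives n = 50 with 85.2% power, which matches the 50 pairs.
- Two independent arms: n per arm = 2 × 47.8 = 95.6, so 96 per arm or 192 in total. This does not match.

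The figure is thus a paired calculation, although the text calls it two-arm. No matching of treated to untreated women is described that would make the pairs anything other than repeated measures.

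**2. Smallest significant rise if the pooled pre/post change decided Aim 3.** Threshold = t(0.975, n−1) × 3/√n.
- N = 80: 0.67 points
- N = 95: 0.61 points
- N = 100: 0.60 points

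These are about half of 1.3.

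**3. Chance of a significant rise with no club effect.** Noncentral t with noncentrality g√n/3, where g is an assumed background or retest gain. The documents give no value for g, so a range is shown.

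| Assumed gain g | N = 80 | N = 100 |
|---|---|---|
| 0 | 2.5% | 2.5% |
| 0.3 | 14% | 17% |
| 0.5 | 31% | 38% |
| 0.65 | 48% | 57% |
| 1.0 | 84% | 91% |

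No parallel figure can be given for Aim 2: the plan states no baseline satisfaction or SD, and does not say whether 20% is relative or in percentage points.

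**4. Precision of the controlled contrast.** For 25 v 25, the standard error is 3 × √(2/25) = 0.849 and 1.3/0.849 = 1.53, so power = Φ(1.53 − 1.96) = 33%. It is 28% at 20 v 20 and 58% at 50 v 50. If 3 is instead the SD of scores, baseline adjustment at assumed pre/post correlations of 0.3, 0.5 and 0.7 gives 36%, 42% and 57% at 25 v 25. These figures ignore clustering by club and do not model the full four-group analysis. The pooled paired test, by comparison, has 97% power at N = 80.

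**5. Who is a control for whom.** Enrolment stops at four groups. Group 2 waits during club 1, group 3 during club 2 and group 4 during club 3. Nobody waits during club 4. The three listed contrasts agree with this; the sentence giving all four groups a wait-list control does not.

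**The case against.** The strongest reply is that the analysis section already puts the control first: paired tests are preliminary and cross-cohort mixed models are primary. A reader might infer that the wait-list plays no part in judging success, and the documents do not support that. Nor do they support the reading that any rise would meet the hypotheses: Aim 2 needs 20%, and Aim 3 needs significance, which is roughly 0.6 to 0.7 points under the assumptions above.

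It is also fair that the drift values are hypothetical. The statements about local services concern supply and report no trend in knowledge. Health education by community health workers is described as limited and confined to nutrition and hygiene, so it is weak evidence of outside gain. This is a pilot, and no go/no-go rule hangs on either hypothesis.

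On group 4, a reader might conclude that these women supply only pre/post data. That is wrong, because the plan uses them as the untreated comparator for group 3. The absence of a control during the last club is inherent in a design in which everyone is eventually treated.

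What survives is the missing link. The hypotheses do not point to the primary analysis, and the treated-versus-untreated contrasts are presented as something that can also be done, not as the deciding test. The sizing arithmetic is paired as well, so the uncontrolled reading is a natural one.

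**Conclusion.** The concern holds as a gap between the hypotheses and the analysis. As worded, Aim 2 is uncontrolled and Aim 3 names no comparator, so a background or retest gain could satisfy them. If the pooled change were used, an assumed 0.5-point gain would pass for success in 31% (N=80) to 38% (N=100) of trials with no club effect. This rests on an SD of change of 3, a two-sided 5% test and an assumed gain; it illustrates the exposure and does not predict drift.

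Two measurement gaps limit how far rewording alone can help. No survey at the end of the wait is described, so the listed contrasts may lack an untreated value at the time the treated group is post-tested; Figure 2 is not shown and may mark one. With satisfaction listed only after the intervention, the Aim 2 change cannot be computed from Table 1 unless the service-use domain contains such items, which is not stated.

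**What to change.** 1. **Aim 3.** State that it is decided by the mixed-model estimate of club versus concurrent untreated participants on SRH knowledge. Label pooled pre/post changes descriptive.
2. **Aim 2.** Apply the same rule only to a satisfaction measure collected at both times. Otherwise call Aim 2 descriptive.
3. **Untreated value.** Confirm which survey supplies it. If Figure 2 shows no end-of-wait survey, either add one or say what is used instead. The enrolment survey of the next group recruited falls at about the right calendar time, but it is a first test in a later cohort and would not remove a retest gain.
4. **Study Design and item 13.** Replace the clause on wait-list controls with, for example: *groups 1 to 3 each have a concurrent wait-list group; group 4 is the untreated comparator for group 3 and has no concurrent control during its own club*.
5. **Power.** Do not attach the 85% figure to the controlled contrast.

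The cost is mostly wording, plus one extra survey for groups 2 to 4 if none is planned at the end of the wait. The real price is precision. With about 33% power for a simple unadjusted 25 v 25 comparison, a significant Aim 3 result becomes much less likely, so the pilot should report the controlled estimate with its confidence interval. Contrasts after round one also involve later-recruited groups and are not purely randomized, which the report should say.
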